7.2 Trial process

7.2.1 Trial Flowchart

7.2.2 Data collecting summary

Number of visits Visit item	Screening stage	Enrollment stage									
	Before operation	Intraoperative	Visit 1	Visit 2	Visit 3	Visit 4	Visit 5	Visit 6	Visit 7	Visit 8	Visit 9
Observation cycle	-30~0d	0d	Before discharge	30±7d	90±14d	180±30d	360±30d	2y±60d	3y±60d	4y±60d	5y±60d
Informed consent form	▲										
Demographic data	▲										
Vital signs	▲		▲	▲	▲	▲	▲	▲	▲	▲	▲
Current medical history	▲										
Past history	▲										
Inclusion/exclusion criteria	▲										
Pregnancy test	▲										
Urine routine	▲										
Blood routine	▲		▲		▲	▲	▲	▲	▲		
Liver function	▲				▲	▲	▲	▲	▲		
Kidney function	▲				▲	▲	▲	▲	▲		
Cardiac enzymes	▲		▲		▲	▲	▲	▲	▲		
Coagulation function	▲										
TTE	▲	▲	▲	▲	▲	▲	▲	▲	▲	▲	▲
Chest X-ray	▲					▲	▲				
ECG	▲		▲	▲	▲	▲	▲	▲	▲	▲	▲
Medication record	▲	▲	▲	▲	▲	▲					

Common complications			▲	▲	▲	▲	▲				
AE			▲	▲	▲	▲	▲	▲	▲	▲	▲
Device deficiencies		▲									

7.2.3 Visit items

7.2.3.1 Medical history and vital signs

Demographic data, current medical history, past medical history and vital signs will be collected.

- (1) Demographic data: sex, date of birth, height and weight
- (2) Vital signs: blood pressure, pulse, body temperature and respiration
- (3) Current medical history: symptom duration and admission time
- (4) Past history: history of allergy, history of dysfunction of important organs (heart, lung, liver and kidney), and history of surgery
- (5) Medication records: CRF only records anticoagulants, antiplatelets and antibiotics

7.2.3.2 Laboratory examination

The subjects must undergo complete laboratory tests before operation. The test items should include at least the following contents:

- (1) Pregnancy test: applicable to women of reproductive age
- (2) Urine routine: urine glucose (GLU), urine protein (PRO), urine red blood cell count (RBC), urine white blood cell count (WBC)
- (3) Blood routine: hemoglobin (Hgb), white blood cell count (WBC), platelet count (PLT), neutrophil percentage (NEUT%)
- (4) Liver function: aspartate aminotransferase (AST), alanine aminotransferase (ALT)
- (5) Kidney function: serum creatinine (Scr), blood urea nitrogen (BUN)
- (6) Cardiac enzymes: Creatine kinase-MB (CK-MB), lactate dehydrogenase (LDH)
- (7) Coagulation function: prothrombin time (PT), activated partial thromboplastin time (APTT), international standardized ratio (INR)

7.2.3.3 Electrocardiogram examination

- (1) ECG

7.2.3.4 Imageological examinations

- (1) Echocardiography

- (2) Chest X-ray

7.2.4 Trial Flowchart

The subjects are required to carry out 9 visits before the end of the trial, specifically as follows:

7.2.4.1 Preoperative (-30 d - 0 d, outpatient/inpatient visit)

- (1) Sign the Informed Consent form
- (2) Demographic data
- (3) Vital signs
- (4) Current medical history
- (5) Past history
- (6) Screening according to the inclusion / exclusion criteria;
- (7) Laboratory tests (pregnancy test, blood routine, coagulation function, urine routine, liver function, kidney function, cardiac enzymes)
- (8) Echocardiography
- (9) Chest X-ray
- (10) ECG
- (11) Medication record

7.2.4.2 Visit 1 (before discharge, hospitalization visit)

- (1) Vital signs
- (2) Laboratory examination (Blood routine, Cardiac enzymes)
- (3) Echocardiography
- (4) ECG
- (5) Medication record
- (6) Common complications
- (7) AE

7.2.4.3 Visit 2 (30 ± 7 days post operation, outpatient visit)

- (1) Vital signs
- (2) Echocardiography
- (3) ECG
- (4) Medication record

(5) Common complications

(6) AE

7.2.4.4 Visit 3 (90 ± 14 days post operation, outpatient visit)

(1) Vital signs

(2) Laboratory examination (Blood routine, Liver function, Kidney function, Cardiac enzymes)

(3) Echocardiography

(4) ECG

(5) Medication record

(6) Common complications

(7) AE

7.2.4.5 Visit 4 (180 ± 30 days post operation, outpatient visit)

(1) Vital signs

(2) Laboratory examination (Blood routine, Liver function, Kidney function, Cardiac enzymes)

(3) Echocardiography

(4) Chest X-ray

(5) ECG

(6) Medication record

(7) Common complications

(8) AE

7.2.4.6 Visit 5 (360 ±30 days post operation, outpatient visit)

(1) Vital signs

(2) Laboratory examination (Blood routine, Liver function, Kidney function, Cardiac enzymes)

(3) Echocardiography

(4) Chest X-ray

(5) ECG

(6) Common complications

(7) AE

7.2.4.7 Visit 6 (2 years ± 60 days post operation, outpatient visit)

(1) Vital signs

- (2) Laboratory examination (Blood routine, Liver function, Kidney function, Cardiac enzymes)
- (3) Echocardiography
- (4) ECG
- (5) AE

7.2.4.8 Visit 7 (3 years ± 60 d post operation, outpatient visit)

- (1) Vital signs
- (2) Laboratory examination (Blood routine, Liver function, Kidney function, Cardiac enzymes)
- (3) Echocardiography
- (4) ECG
- (5) AE

7.2.4.9 Visit 8 (4 years ± 60 d post operation, outpatient visit)

- (1) Vital signs
- (2) Echocardiography
- (3) ECG
- (4) AE

7.2.4.10 Visit 9 (5 years ± 60 d post operation, outpatient visit)

- (1) Vital signs
- (2) Echocardiography
- (3) ECG
- (4) AE

7.2.5 Medication guidance

- (1) Postoperative heparin anticoagulation for 24 hours;
- (2) Oral administration of Aspirin 3-5 mg/(kg.d) for children and 3 mg/(kg.d) for adults until 6 months post operation.
- (3) Use of antibiotics within 30 min before operation.

7.3 Monitoring plan

According to the requirements of *Good Clinical Practice for Medical Devices*, the sponsor should select qualified clinical research associates to perform the monitoring duties on all participating institutions. The number of clinical research associates and the monitoring frequency depend on the complexity of clinical trial and the

number of participating institutions in the trial. The specific responsibilities include:

- (1) Validate whether the clinical trial institution has proper conditions before the trial, including whether the staffing and training meet the requirements, whether the laboratory is fully equipped and in good working condition, and whether a sufficient number of subjects are expected, and whether the participating investigators are familiar with the trial requirements;
- (2) Check whether the clinical trial institutions and investigators comply with relevant laws and regulations, *Good Clinical Practice for Medical Devices* and clinical trial protocol before, during and after the trial;
- (3) Confirm whether each subject signs an informed consent form before participating in the clinical trial, and understand the selection of subjects and the progress of the trial. The visits, tests and examinations that the investigators fail to do, and whether mistakes and omissions are corrected, should be clearly and truthfully recorded. For revision of informed consent form, the affected subjects who have not finished the clinical trial process should be re-signed the form;
- (4) Confirm that all case report forms are filled in correctly and consistent with the original data, and all errors or omissions have been corrected or noted, signed and dated by the investigators; Confirm and record the disease type, total number of cases, sex, age and therapeutic effect of each trial;
- (5) Confirm that withdrawal from the clinical trial or failure to comply with the requirements of the informed consent form are recorded, and discuss such situations with the investigators;
- (6) Confirm that all AEs, complications and other device defects are recorded, and SAEs and device defects that may lead to SAEs are reported and recorded within the specified time;
- (7) Monitor the supply, use, maintenance, transportation, receiving, storage, distribution, processing and reclaiming of the test device;
- (8) Monitor the regular maintenance and calibration of relevant equipment during clinical trial;
- (9) Ensure that all clinical trial related documents received by investigators are the latest versions;
- (10) A written report should be submitted to the sponsor after each monitoring. The report should include the name of the clinical research associates, date, time, place, contents, investigator name, project completion status, existing problems, conclusions and corrections to errors and omissions.

8. Statistical considerations

8.1 Statistical design, methods and analysis procedures

The study is a prospective, multi-center and single-arm OPC design clinical trial. In this study, two primary endpoints are set, namely:

- (1) Primary safety endpoint (low-priority index) -- Rate of common complications during 360-day post operation;

(2) Primary efficacy endpoint (high-priority index) -- Effective closure rate at 360-day post operation;

The two indexes in the trial are treated according to the co-primary endpoint. Only when both indexes reach the OPC can it be concluded that the investigational device meets the clinical application requirements.

8.2 Sample size calculation

8.2.1 Total sample size

This clinical trial plans to recruit 146 subjects. The sample size determination process is as follows:

This clinical trial adopts single-arm OPC design and uses effective closure rate at 360-day post operation and the rate of common complications during 360-day post operation as the basis for sample size estimation.

[figure not shown]
At present, the technique of ASD occlusion is mature and widely used in clinic. A large number of clinical data, large-scale clinical trials, randomized controlled trials and systematic evaluations (Meta analyses) of traditional metal products on the market have proved the safety and efficacy of this treatment (advantages compared with the surgery). The literature data are shown in the table below.

Clinical Trial to Evaluate the Safety and Efficacy of Absnow™ Absorbable ASD Closure System for ASD Patients

[figure not shown]
Literatures	Publishing date	Device name	Effective closure rate at 360-day post operation	Rate of common complications during 360-day post operation	Sample size
Zhong-Dong Du, et al. ^[1]	2002	Amplatzer Septal Occluder	98.5%	0.65%	288
Shinichi Oho, et al. ^[2]	2002	Amplatzer Septal Occluder	97%	2.86%	35
Sergio Luiz Navarro Braga, et al. ^[3]	2004	Amplatzer Septal Occluder	95.8%	4.1%	49
Cristiano Oliveira Cardoso, et al. ^[4]	2006	Amplatzer Septal Occluder	93%	3.96%	101
Thomas K. Jones, et al. ^[5]	2007	GORE HELEX Septal Occluder	98.1%	3.4%	119
Allen D. Everett, et al. ^[6]	2009	Amplatzer Septal Occluder	96%	0.9%	478
Tehmina Kazmi, et al. ^[7]	2009	Amplatzer Septal Occluder	99%	3.5%	204
Alexander J. Javois, et al. ^[8]	2014	GORE HELEX Septal Occluder	96.7%	--	137
Sukman T. Putra, et al. ^[9]	2015	Amplatzer Septal Occluder & Lifetech Heart ASD occluder	96.37%	2.6%	152
Daniel R. Turner, et al. ^[10]	2017	Amplatzer Septal Occluder	98.21%	1.6%	1000

1) Effective closure rate at 360-day post operation

Combining (Meta-analysis) of the one-year effective closure rates reported in each of the above documents shows that the one-year treatment success rate of the traditional metal ASD closure system is 98%, and the 95% CI is [97%, 99%].

[figure not shown]

Combining (Meta-analysis) of the lower limits of 95% CI of one-year effective closure rates of each of the above documents shows that 95% CI of lower limits of 95% CI of one-year effective closure rates of traditional metal ASD closure system is [94%, 97%].

[figure not shown]

2) Rate of common complications during 360-day post operation

Combining (Meta-analysis) of the rates of common complications within one year reported in each of the above documents shows that the rate of common complications within one year is 1%, with a 95% CI of [1%, 2%].

Combining (Meta-analysis) of the upper limits of 95% CI of the rates of common complications in each of the above documents within one year shows that the 95% CI of the upper limits of 95% CI of the rate of common complications in the traditional metal ASD closure system within one year is [2%, 5%].

According to the summary of the results reported in the literatures, the treatment success rate at 360-day post operation of the ASD closure systems made of traditional metal materials ranged from 93% to 99%, and the rate of common complications during 360-day post operation was between 0.65% and 4.1%. Considering that the ASD closure systems made of traditional metal materials have been on the market for nearly 20 years, the industry has rich interventional experience and the treatment has confirmed efficacy and predictable incidences of common complications. In China, Lifetech Scientific has taken the lead in using absorbable materials that have good biocompatibility to develop novel ASD closure system and applied it for clinic use for the first time. At present, there is still no similar product on the market. Despite the relevant quality control measures, in multi-center clinical trials, there may still be differences in clinical practices (such as interventional techniques and evaluation experience) among different centers, resulting in different effects among different centers, especially the surgeon's learning curves, which will not only affect the proficiency of operations but also the efficacy of the investigational device and the prediction of common complications to a certain extent. In addition, we hope this study can make the clinical efficacy evaluation of the investigational device more realistic, fully understand the differences between the clinical practice of ASD occlusion with novel absorbable materials and the consensus of experts in the ASD occlusion with existing traditional metal occluders, provide objective comparative basis for clinical selection of novel absorbable ASD closure system, and also provide reference for the formulation and standardization of occlusion guidelines with novel absorbable materials in the future. Therefore, according to the results of meta analyses, clinical experience and primary endpoints defined in this trial after full discussion with clinical experts and statistical experts, the target and OPC of Absnow™ ASD closure system are set as follows:

Endpoints	Target	Unilateral boundary value of 95% CI (OPC)
Effective closure rate at 360-day post operation	99%	94%
Rate of common complications during 360-day post operation	1%	6%

Sample size is estimated by SAS9.4 software, and the operation is as follows:

- a) Effective closure rate at 360-day post operation

```
proc power;
onesamplefreq
test = z
method = normal
nullproportion = 0.94
proportion = 0.99
sides = U
power = 0.8
alpha = 0.025
ntotal = . ;
run;↵
```

The POWER Procedure
Z Test for Binomial Proportion

Fixed Scenario Elements	
Method	Normal approximation
Number of Sides	U
Null Proportion	0.94
Alpha	0.025
Binomial Proportion	0.99
Nominal Power	0.8
Variance Estimate	Null Variance

Computed N Total	
Actual Power	N Total
0.802	121

The target and OPC of effective closure rate at 360-day post operation are set as 99% and 94%, respectively. SAS software calculation indicates that at least 121 patients are needed. Considering a dropout rate of 20%, 146 patients are required.

b) Rate of common complications during 360-day post operation

```
proc power;
onesamplefreq
test = z
method = normal
nullproportion = 0.06
proportion = 0.01
sides = L
power = 0.8
alpha = 0.025
ntotal = . ;
run; ↵
```

The POWER Procedure
Z Test for Binomial Proportion

Fixed Scenario Elements	
Method	Normal approximation
Number of Sides	L
Null Proportion	0.06
Alpha	0.025
Binomial Proportion	0.01
Nominal Power	0.8
Variance Estimate	Null Variance

Computed N Total	
Actual Power	N Total
0.802	121

The target and OPC of rate of common complications during 360-day post operation are set as 1% and 6%, respectively. SAS software calculation indicates that at least 121 patients are needed. Considering a dropout rate of 20%, 146 patients are required.

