8.3 Significance level and power

This trial adopts single-arm design and the significance level α (one-sided) = 0.025, and the power is 80%.

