3. STUDY PLAN

3.1. Study Design

This study is designed as a prospective, multicenter, single-arm trial. Through screening, subjects meeting the inclusion and exclusion criteria will be enrolled and undergo implantation of the Absnow™ Absorbable ASD Closure System to assess the safety and efficacy of this study device.

This study plans to enroll 142 subjects from 14 sites in China, and each site will enroll no more than 50% of the total subjects. After undergoing the procedure, follow-up visits will be conducted at nine time points: Before discharge, 30 days, 90 days, 180 days, 360 days, 2 years, 3 years, 4 years, and 5 years post-procedure. An interim analysis of the study will be conducted using the follow-up data obtained within 360 days post-procedure. The results of this interim analysis will be used to support the submission of a marketing authorization application to the National Medical Products Administration (NMPA).

Before the official launch of the nationwide multicenter study, a pilot study with a planned enrollment of 5 subjects will be conducted. Data from these subjects will not be included in the overall efficacy analysis population or the final sample size calculation.

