5.1.1. Primary efficacy endpoints

Primary efficacy endpoint is effective closure rate at 360-day post operation. Effective closure is defined as no or only a trivial to small residual shunt (based on left-to-right Doppler flow signals with a diameter <5mm) as assessed by TTE or TEE after device implantation.

For the primary efficacy endpoint evaluation, the following hypotheses are tested:

Null hypothesis $H_0: \pi_1 \leq \pi_0$. That is, the Absnow Absorbable Atrial Septal Defect Occluder System fails to meet the design requirement for the 360-day post-operation effective closure rate.

Alternative hypothesis $H_1: \pi_1 > \pi_0$. That is, the Absnow Absorbable Atrial Septal Defect Occluder System meets the design requirement for the 360-day post-operation effective closure rate.

π_1 refers to the expected 360-day post-operation effective closure rate, π_0 refers to the Objective Performance Criteria (OPC) value of 360-day post-operation effective closure rate

Statistical inference will be performed using the exact method to estimate the 95% confidence interval (CI) for the effective closure rate at 360 days post-operation, as well as the P-value for comparison with the predefined performance goal of 94%. If the lower limit of the two-sided 95% CI for the effective closure rate at 360 days exceeds 94%, the null hypothesis will be rejected, and it will be concluded that the Absnow Absorbable Atrial Septal Defect Occluder System meets the

design requirement for the 360-day post-operation effective closure rate. Otherwise, it cannot be concluded that the 360-day effective closure rate meets the predefined performance requirement.

If a subject has missing valid data at 360 days, the subject will be imputed as “ineffective” using the Non-responder Imputation (NRI) method. For analyses based on the PPS, missing data will not be imputed.

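### The stated power of 0.802 at N=121 is a normal approximation; the planned exact test has 0.878 there, and the approximation hides the cost of 142 subjects against 146

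*Protocol*

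**What the plan says.** Protocol 8.2.1 runs the SAS power procedure once per primary endpoint, with a z test, the normal method and the null variance. The efficacy run uses "nullproportion = 0.94" and "proportion = 0.99"; the safety run uses "nullproportion = 0.06" and "proportion = 0.01". Both have one-sided alpha 0.025 and both return N=121 with power 0.802: "SAS software calculation indicates that at least 121 patients are needed". A 20% dropout allowance then raises 121 to 146. Protocol 8.3 summarises the design as one-sided 0.025 "and the power is 80" per cent.

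Protocol 8.5 and 8.7.4 ask for a 95% confidence interval without naming a method. SAP 5.1.1 names it: "Statistical inference will be performed using the exact method to estimate the 95% confidence interval (CI"). SAP 5.1.2 does the same for complications. Success needs the lower exact limit for closure above 94% and the upper exact limit for complications below 6%.

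SAP 3.1 has a different size: "This study plans to enroll 142 subjects from 14 sites in China". Neither document gives the power of the exact test, or any power at 142.

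**The concern.** With about one expected failure, the pass rule is a small whole number: 2 failures allowed, or 3. True power moves in steps. It jumps when one more failure becomes allowable and drifts down until the next jump. A smooth normal formula cannot show this, so its power figure need not match the power of the test that will be run, and it is a poor guide when N changes.

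The SAP's 142 makes this practical. On the protocol's formula a cut of four subjects looks almost free. If it removes one of three allowable failures on each of two endpoints that must both succeed, whoever chose 142 would have had no way to see that from the printed calculation.

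**Working it through.** **Inputs.** From protocol 8.2.1: null failure rate 0.06 and assumed failure rate 0.01 for complications, and the mirror image (1−0.94 and 1−0.99) for closure, so one calculation serves both. From 8.2.1 and 8.3: one-sided alpha 0.025. From SAP 5.1.1 and 5.1.2: exact two-sided 95% limits.

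**Step 1: reproduce the printed figure.** Power = Φ[(0.05 − 1.96·√(0.06·0.94/N)) / √(0.01·0.99/N)]. At N=121 the two standard errors are 0.02159 and 0.00905, so power = Φ(0.850) = 0.802. Solving for 80% gives N=120.65, hence 121. The protocol's output is correct for the method it names. The same formula gives 0.905 at 142 and 0.918 at 146.

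**Step 2: exact rule.** The exact upper limit is below 6% when the failure count is at most c, the largest c with P(X≤c | N, 0.06) ≤ 0.025. Power is P(X≤c | N, 0.01).

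- N=121: expected failures 121×0.01 = 1.21. c=2, one-sided error 0.0215. Power = 0.2964 + 0.3623 + 0.2195 = 0.878.
- N=142: c=2, because three failures give an upper limit of 6.05%. Error 0.0078. Power = 0.2400 + 0.3442 + 0.2451 = 0.829.
- N=146: c=3, upper limit 5.89%. Error 0.0221. Power = 0.2305 + 0.3400 + 0.2490 + 0.1207 = 0.940.

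**Step 3: over a range of analysed sizes** (per endpoint, no missing data).

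| N | Allowed failures | One-sided error | Exact power | z formula |
|---|---|---|---|---|
| 117 | 1 | 0.0061 | 0.673 | 0.776 |
| 118 | 2 | 0.0247 | 0.885 | 0.783 |
| 121 | 2 | 0.0215 | 0.878 | 0.802 |
| 138 | 2 | 0.0095 | 0.839 | 0.890 |
| 140 | 2 | 0.0086 | 0.834 | 0.898 |
| 142 | 2 | 0.0078 | 0.829 | 0.905 |
| 143 | 2 | 0.0074 | 0.827 | 0.908 |
| 144 | 3 | 0.0242 | 0.943 | 0.912 |
| 146 | 3 | 0.0221 | 0.940 | 0.918 |

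The formula understates power at 121 and overstates it at 142. From 118 to 499 the lowest exact power is 0.827, at 143.

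**Step 4: where the gap comes from.** A one-sided z test with null variance rejects when the failure count is at most 0.06N − 1.96·√(0.0564N). That bound is 2.14 at 121, 2.97 at 142 and 3.14 at 146, so the test allows 2, 2 and 3 failures, the same counts as the exact rule. Between 138 and 146 the two rules differ only at 143. The error therefore lies in approximating the power of a discrete test, not in choosing an exact test over a z test.

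**Step 5: missing data.** SAP 4.2 counts a missing 360-day result as a failure. With m missing, power = P(X≤c−m | N−m, 0.01). For m=1 this is 0.588 at 142 and 0.822 at 146; for m=2 it is 0.245 and 0.577. Three missing subjects make success impossible at 142.

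**The case against.** The best reply is that nothing here is miscalculated and nothing falls short. The figure 0.802 is the right output of the method printed beside it. At the planning size the error is on the safe side, since true power is higher than stated. At 121, 142 and 146 alike, exact power with complete data exceeds the 80% that protocol 8.3 promises for a single endpoint. All of that stands.

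Three stronger readings should be set aside:

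- A reader might infer that 142 is underpowered on an endpoint. The documents' own assumptions give 0.829, above target.
- A reader might blame the SAP's exact method for the lost failure. A z test allows the same counts at 121, 142 and 146.
- A reader might conclude that the analysed N should be fixed at 144 to 146, with at most 3 failures written in as the pass rule. The sponsor cannot fix it. The full analysis set (protocol 8.9, SAP 4.1.1) leaves out subjects whose implantation is abandoned for other clinical reasons, and successfully implanted subjects with no post-baseline primary endpoint data. With 146 enrolled, three exclusions give 143, the lowest point in the table.

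It is also fair that 142 against 146 is in itself an inconsistency between documents. It belongs here because the protocol's formula prices it at 1.3 points when the real price is 11.

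**Conclusion.** The point holds as a misstated power figure together with an unexplained difference in sample size. The planned test has power 0.878 at N=121, not 0.802. Moving from 146 to 142 costs 11 points of power and one allowable failure per endpoint (0.940 to 0.829), where the protocol's method shows 0.918 to 0.905.

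These figures assume true rates of exactly 99% and 1%, an analysis set equal to the stated N, no missing data, and one endpoint at a time. Both endpoints must succeed. If they were independent, joint power would be 0.829² = 0.688 at 142 and 0.940² = 0.884 at 146. They overlap, because a residual shunt of 5 mm or more counts against both, so joint power should lie between those values and the single-endpoint ones. For the same reasons, 0.940 should not be quoted as what 146 delivers: one missing subject already lowers it to 0.822.

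**What to change.** - In protocol 8.2.1 and 8.3, replace the z-test output with exact binomial power for the test in SAP 5.1.1 and 5.1.2.
- Tabulate it over plausible full-analysis-set sizes, for example 138 to 146, with the allowable failure count and the actual one-sided error at each.
- State that the figures are per endpoint with no missing data, and add how they fall when missing subjects count as failures (one missing: 0.588 at 142, 0.822 at 146).
- Reconcile the 142 in SAP 3.1 with the protocol's 146, giving the reason for whichever figure is kept.
- Keep the SAP's exact-interval decision rule, which adapts to the realised N. Give the failure counts as illustration, not as a fixed pass rule.

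The cost is two reruns of the power procedure with the exact test, one short table and edited text in three sections. No change to the endpoints or the decision rule is needed.

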7.1.5.3 Dropout Criteria and management

Subjects who have signed informed consent forms and are screened qualified quit the trial and fail to complete the observation period specified in the protocol are called dropout cases, regardless of when and why. The criteria for dropout are as follows:

- (1) For whatever reason, the subject is unwilling or impossible to continue the clinical trial, and requires to withdraw from the clinical trial.
- (2) Although the subject does not explicitly propose to withdraw from clinical trial, he/she no longer receive treatment and examination and loses to follow-up
- (3) The subject presents SAE, and the investigator judges that the subject should withdraw from the clinical trial.
- (4) The subject has poor compliance.

Dropout management: For all dropout cases, the summary form of clinical trial completion should be filled in the original records and the reasons for dropout should be analyzed. When the subject drops out, the investigator should contact the subject as much as possible, inquire the reason and record the last clinical symptom, and complete the evaluation items that can be achieved. If the subject withdraws from the trial due to AE, the investigator should take corresponding treatment actions according to the actual situation of the subject.

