8.4 Expected dropout rate

- (1) Dropout refers to the early withdrawal of the subjects during the clinical trial because of various reasons. For example, patients voluntarily withdraw the informed consent, lose follow-up and cannot complete the whole process of clinical trials due to AEs.
- (2) In the process of sample size estimation, the expected maximum dropout rate is set at 20%, which refers to the proportion of dropout cases.

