8.7.2 Missing and unreasonable data

The trial should ensure that the data records are 100% correct, especially the primary endpoints. For missing, unused and irrational data or data of withdrawal subjects, strict review should be conducted. The basic statistical principles for processing these data are as follows:

- (1) The details of each dropout subject will be described;
- (2) The last observation carried forward (LOCF) method will be applied for the missing values of the main evaluation indicators;
- (3) The missing values of qualitative or quantitative secondary endpoints are not carried forward, and are

handled according to the missing values;

- (4) The missing values of all safety endpoints are not carried forward, and are handled according to the missing values.

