10.2 Analysis of the likelihood of failure

- (1) There are too many subjects who quit the trial due to SAEs;
- (2) Subjects who lose to follow-up account for more than 20% of the sample size;
- (3) IFU and labeling information of the device cannot effectively guide the operator;
- (4) Serious safety problems are found during the trial;
- (5) Major mistakes are found in the protocol during the trial, leading to difficulty in evaluating the product efficacy;
- (6) The operation of the trial personnel is unskilled.

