4.1.1. Full Analysis Set (FAS)

Full analysis set (FAS): According to the basic principles of Intention to Treat (ITT), FAS refers to the set of subjects that comply with the ITT principles. It includes:

- a) Subjects who have been treated with the investigational device, achieved the immediate operation success, and have at least one observation data of primary endpoints after baseline;

- b) Subjects who have received treatment with the investigational device, but have failed in the implantation because of the device itself, regardless of whether there is a study device in the body.

If the implantation is abandoned due to other clinical reasons and there is no investigational device in the body, such subject will not be included in the FAS. The definition of receiving the investigational device treatment is that if any part of the device, including the occluder itself and its delivery device, contact with human body through vascular approach, it can be considered as receiving the device treatment. FAS will be the main data set for baseline data analysis, primary safety, and efficacy evaluation.

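### The dropout inflation to 146 does not match the protocol's own definition of 20% dropout, the SAP plans 142 without a derivation, and the stated 80% power was never recomputed for the SAP's primary analysis

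*Protocol*

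**What the plan says.** **Sizing.** Protocol 8.2.1 uses a one-sample z test for each primary endpoint: 94% against 99% for effective closure, 6% against 1% for common complications, one-sided alpha 0.025, power 80%. Each calculation gives 121. For each endpoint the protocol then adds: "Considering a dropout rate of 20%, 146 patients are required".

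**Meaning of the 20%.** Protocol 8.4 says "the expected maximum dropout rate is set at 20%, which refers to the proportion of dropout cases". Protocol 7.1.5.3 describes dropouts as subjects who "fail to complete the observation period specified in the protocol are called dropout cases, regardless of when and why". Protocol 10.2 lists as a route to failure: "Subjects who lose to follow-up account for more than 20% of the sample size". That line does not define the allowance, but it also treats 20% as a share of the sample.

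**Enrolment in the SAP.** SAP 3.1 says "This study plans to enroll 142 subjects", with no calculation, dropout rate or power.

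**Missing data.** Protocol 8.7.2, item 2: "The last observation carried forward (LOCF) method will be applied for the missing values of the main evaluation indicators". Item 4 of the same section: "The missing values of all safety endpoints are not carried forward". SAP 4.2 instead counts a subject with missing day-360 data as a closure failure, and one with incomplete safety follow-up as having had a complication. SAP 5.1.1 and 5.1.2 test both endpoints in the FAS with exact two-sided 95% intervals against 94% and 6%. Both must pass.

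**The concern.** Multiplying by 1.2 replaces a loss equal to 20% of those needed, not 20% of those enrolled. Because the protocol defines the allowance as a proportion of dropouts, 146 enrolled with 20% lost leaves fewer than the 121 that the calculation requires. The SAP then uses a different enrolment number with no derivation.

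A second gap matters more. The 80% power and 20% dropout figures belong to a z test in which dropouts are simply replaced. The SAP decides the trial by another analysis, in which each missing subject counts as a failure on both primary endpoints. With targets this close to 100% and 0%, very few failures are affordable. A sponsor relying on the protocol's figures could believe that a 20% loss is covered when a handful of missing day-360 visits would decide the result.

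**Working it through.** **Inputs.** p0 = 0.94, p1 = 0.99 (0.06 and 0.01 for safety give identical results), one-sided alpha 0.025, power 0.80, dropout 20% (Protocol 8.2.1, 8.3, 8.4). Enrolment 146 (Protocol 8.2.1) and 142 (SAP 3.1).

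**1. Reproduce 121.** n = (1.960·√(0.94·0.06) + 0.8416·√(0.99·0.01))² / 0.05² = 120.65, so 121. Power at 121 is 0.802, as the protocol prints.

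**2. Dropout inflation.**
- 121 × 1.2 = 145.2, so 146: the protocol's figure.
- 121 / (1 − 0.20) = 151.25, so 152: the figure that fits Protocol 8.4.
- Loss that still leaves 121: 1 − 121/146 = 17.1%; 1 − 121/142 = 14.8%.

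**3. Power if dropouts are removed and the full 20% is lost by day 360.** Power(n) = Φ((0.05·√n − 1.960·√0.0564)/√0.0099).
- 146 × 0.8 = 116.8: 76.9% at 116, 77.6% at 117.
- 142 × 0.8 = 113.6: 74.7% at 113, 75.4% at 114.

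**4. Power under LOCF with every dropout kept and a 99% rate.** The same formula gives 91.8% at 146 and about 90% at 142.

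**5. SAP primary analysis.** Assume that the FAS equals enrolment and that missingness (rate m) is independent of outcome.
- The largest number of failures whose Clopper-Pearson upper limit is below 6%: 3 at 146 (3/146 gives 5.89%) and 2 at 142 (3/142 gives 6.05%). The limit is 2 for an FAS of 118 to 143 and 3 for 144 to 167, so 152 still allows only 3.
- Probability that a subject counts as a failure: q = 1 − 0.99·(1 − m). Per-endpoint power = P(Binomial(N, q) ≤ limit).

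| Missing at day 360 | q | N = 142 (limit 2) | N = 146 (limit 3) | N = 152 (limit 3) |
|---|---|---|---|---|
| 0% | 0.0100 | 83% | 94% | 93% |
| 1% | 0.0199 | 46% | 67% | 64% |
| 2% | 0.0298 | 20% | 36% | 33% |
| 5% | 0.0595 | 1% | 2% | 2% |

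- Four missing subjects at 146, or three at 142, fail both endpoints whatever the other subjects show.
- q reaches the 6% OPC when m = 1 − 0.94/0.99 = 5.05%. At 20% missing, q = 1 − 0.99 × 0.8 = 20.8%.

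**6. Both endpoints together, nothing missing.** If failures fully overlap, joint power equals the per-endpoint figure (94% at 146, 83% at 142). If true failures are independent, it is 0.940² = 88% at 146 and 0.829² = 69% at 142.

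**The case against.** The strongest reply is that the headline shortfall need not occur. The protocol does not remove dropouts from the FAS efficacy analysis: its written rule is LOCF, and 80% per endpoint then holds comfortably. The 20% is also a maximum over an observation period that runs to five years, whereas both endpoints are read at day 360, and 146 covers a 17.1% loss by then.

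This stands. A reader might infer from the slip that the trial has only 77% or 75% power. The documents do not support that: those figures need both removal of dropouts and the whole 20% lost by day 360. What the reply does not settle is the primary safety endpoint, because Protocol 8.7.2 item 2 reads as carrying it forward and item 4 bars carry-forward for safety endpoints. Nor does it make 146 follow from the stated definition.

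Three other inferences should be resisted:
- That the SAP promises 80% power with 20% dropout. It states neither figure; they are the protocol's, and they were not updated when the analysis rule changed.
- That joint power must be close to per-endpoint power because failures overlap. A shunt of 5 mm or more at day 360 fails both endpoints, as does a missing subject. The other six listed complications need not affect closure, and the documents do not break down the 1%.
- That 142 can be traced to a particular calculation. No derivation is given.

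Taking the FAS as equal to enrolment is also a simplification. For a subject whose implantation is abandoned for other clinical reasons with no device left in the body, SAP 4.1.1 says "such subject will not be included in the FAS". Three such exclusions from 146 leave 143, where the limit falls from 3 failures to 2.

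**Conclusion.** The concern holds in two separate parts.

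**Arithmetic and consistency.** 146 does not follow from 121 with a 20% dropout proportion; 152 does, a gap of 6 subjects. The protocol and SAP give different enrolment numbers, and 142 is not derived. In the worst case of step 3 the cost is about 3 percentage points of per-endpoint power at 146 and about 5 at 142. Under LOCF with all dropouts kept there is no shortfall. This part is modest.

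**Power of the deciding analysis.** The protocol's pairing of 80% power with 20% dropout cannot hold for the SAP's exact analysis with missing counted as failure. At 146, per-endpoint power is below 80% with 1% missing and about 2% with 5% missing; 142 is worse at each rate. From about 5.05% missing the expected failure rate is at or above the OPC, so no sample size helps. This comes from the analysis rule, not from the inflation slip, and enrolling 152 does not cure it. The figures assume true rates of 99% and 1%, an FAS equal to enrolment, and missingness independent of outcome.

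**What to change.** - State one enrolment number, with its derivation, in both documents.
- In Protocol 8.2.1, 8.3 and 8.4, either restate the dropout allowance (about 17% for 146, about 15% for 142) or restate the power at 20%. Give the loss expected by day 360 separately from the maximum over the whole observation period.
- Name one missing-data rule for each primary endpoint, identical in the protocol and the SAP, and resolve items 2 and 4 of Protocol 8.7.2 for the primary safety endpoint.
- State that the protocol's 80% and 20% figures do not apply to the SAP's exact, missing-as-failure analysis. Add to the SAP a short table of the maximum allowable failures (missing included) by FAS size, with exact power over a range of day-360 missing rates.
- State that 80% is per endpoint and that both must pass, and give joint power as a range: with nothing missing, 88% to 94% at 146 and 69% to 83% at 142, from independent true failures to full overlap.

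The cost is revised text in three protocol sections, the missing-data wording, and one number and one table in the SAP. No extra patients are needed if the dropout and power figures are restated.
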